FEND II: Fexofenadine Hydrochloride Study Protocol for MI Prognosis

Study Protocol

The Impact of Fexofenadine Hydrochloride on the Prognosis of Patients Post-Acute Myocardial Infarction: A Randomized Clinical Trial (FEND II)

FEND II Study Protocol

Version No.: V1.3

December 15, 2025

Principal Investigator:

[name]

Department of Cardiovascular Medicine,

The Second Affiliated Hospital of Zhejiang University School of Medicine

National Key Laboratory of Transvascular Implantable Devices

[name]

E-mail: [contact]

1. Study Background

Myocardial infarction (MI) and subsequent heart failure are among the leading causes of death in patients with cardiovascular diseases in China. Myocardial cell death following MI triggers the activation of fibroblasts. Although fibroblasts play a reparative role, their excessive activation and the overdeposition of extracellular matrix can form fibrotic tissue, ultimately leading to heart failure. Currently, while a series of measures can reduce early mortality after MI, there is a lack of effective therapeutic approaches targeting pathological fibrosis post-MI. Therefore, inhibiting the excessive activation of cardiac fibroblasts and reducing cardiac fibrosis after MI are crucial scientific issues and clinical needs that urgently require resolution.

Although the mechanisms driving organ-specific fibrosis have not been fully elucidated, fibrosis in different tissues and organs is characterized by the persistent abnormal activation of myofibroblasts mediated by multiple signals such as transforming growth factor (TGF), platelet-derived growth factor (PDGF), and fibroblast growth factor (FGF). Drugs targeting these abnormal signals have achieved certain efficacy in clinical trials, such as nintedanib and pirfenidone. Our preliminary work found that the expression of flavin-containing

monooxygenase 2 (FMO2) in cardiac tissue is significantly reduced after MI. Downregulation of FMO2 in cardiac fibroblasts leads to impaired cardiac function, increased collagen deposition, and aggravated fibrosis, suggesting that FMO2 can also serve as a therapeutic target for cardiac fibrosis.

Through high-throughput screening of the FDA drug library, we previously identified that fexofenadine hydrochloride significantly promotes FMO2 expression. Fexofenadine hydrochloride is a third-generation H1 receptor antagonist primarily used for the treatment of allergic diseases such as seasonal allergic rhinitis and chronic idiopathic urticaria¹⁰. However, the efficacy and safety of fexofenadine hydrochloride in the treatment of acute myocardial infarction remain unclear. Our preliminary mouse studies demonstrated that fexofenadine hydrochloride can significantly improve cardiac function and reduce fibrosis after MI in mice, with no significant adverse effects on liver and kidney function within the effective dose range. We also verified the safety of this drug in human cardiac organoids. Furthermore, we initiated a prospective, multicenter, randomized controlled clinical trial to evaluate the efficacy and safety of fexofenadine hydrochloride in patients with acute ST-segment elevation myocardial infarction (STEMI). Based on this, the present clinical study aims to assess the efficacy and safety of fexofenadine hydrochloride in improving the prognosis of acute MI.

2. Study Objectives

To evaluate the prognostic effect of fexofenadine hydrochloride in patients with MI through a large-sample, multicenter randomized controlled study.

3. Study Design and Methods

3.1 Study Design

An investigator-initiated, multicenter, double-blind, placebo-controlled, superiority randomized controlled clinical trial. Participating centers include: The Second Affiliated Hospital of Zhejiang University School of Medicine, Ruijin Hospital Affiliated to Shanghai Jiao Tong University School of Medicine, Fuwai Central China Cardiovascular Hospital, West China Hospital of Sichuan University, The First Affiliated Hospital of Wenzhou Medical University, The Second Affiliated Hospital of Wenzhou Medical University, The First Affiliated Hospital of Harbin Medical University, The Second Affiliated Hospital of Chongqing Medical University, etc.

Additional study sites may be added subsequently.

3.2 Patient Enrollment

Patients with acute ST-segment elevation myocardial infarction (STEMI) will be enrolled from multiple centers and randomly assigned to the fexofenadine treatment group or the placebo group.

3.3 Study Period

Recruitment period: 24 months. Follow-up time points: 6th, 12th, 24th, and 60th months after enrollment.

3.4 Inclusion Criteria

1. Age \geq 18 years old.
2. Able to verbally confirm understanding of the trial risks, benefits, and treatment options of fexofenadine hydrochloride therapy. He/she or his/her legal representative must provide written informed consent prior to participating in the clinical trial.
3. Acute ST-segment elevation myocardial infarction (STEMI) occurring within 7 days, with diagnostic criteria including:
 - i) Typical clinical symptoms: such as severe crushing pain in the retrosternal or precordial area, usually lasting more than 10-20 minutes, which may radiate to the left upper arm, jaw, neck, back, or shoulders, etc.;
 - ii) Elevated serum cardiac troponin (cTn): at least one measurement above the upper limit of normal (99th percentile of the reference upper limit);
 - iii) ST-segment elevation: new ST-segment elevation at the J point in 2 adjacent leads.
4. Echocardiography indicating segmental wall motion abnormalities.

3.5 Exclusion Criteria

1. Need for long-term use of fexofenadine hydrochloride or other H1 receptor inhibitors.
2. Previous coronary artery bypass grafting (CABG) surgery.
3. History of severe renal failure with estimated glomerular filtration rate (eGFR) < 30 ml/min.
4. History of severe liver dysfunction.
5. History of concurrent severe infection, hepatobiliary obstruction, or malignant tumor.
6. Expected life expectancy of less than 2 years due to non-cardiac diseases.
7. Currently receiving immunosuppressive therapy.
8. Pregnant, potentially pregnant, or lactating women.
9. Contraindication to the study drug or examinations.
10. Failure to provide written informed consent.
11. Presence of mechanical complications (ventricular septal defect, papillary muscle dysfunction, acute mitral regurgitation), refractory cardiogenic shock unresponsive to vasopressors, acute left heart failure or pulmonary edema, or malignant arrhythmias uncontrolled by antiarrhythmic drugs at enrollment.

3.6 Patient Follow-up

Clinical follow-up will be conducted via telephone or outpatient visits at 6th, 12th, 24th, and

60th months after enrollment.

3.7 Primary Endpoint

Incidence of major adverse cardiovascular and cerebrovascular events (MACCE) within 24 months after randomization, including all-cause death, recurrent myocardial infarction, stroke, hospitalization for heart failure, outpatient or emergency visits due to worsening heart failure, and repeat revascularization driven by angina pectoris.

3.8 Secondary Endpoints

1. All-cause death at 24 and 60 months after randomization.
2. Recurrent myocardial infarction at 24 and 60 months after randomization.
3. Stroke at 24 and 60 months after randomization.
4. Hospitalization for heart failure or outpatient/emergency visits due to worsening heart failure at 24 and 60 months after randomization.
5. Repeat revascularization driven by angina pectoris at 24 and 60 months after randomization.
6. Comparison of the difference in left ventricular ejection fraction (LVEF%) measured by echocardiography between the two groups at 24 months after randomization compared to baseline.
7. Comparison of the difference in left ventricular end-systolic diameter (LVIDs) measured by echocardiography between the two groups at 24 months after randomization compared to baseline.
8. Comparison of the difference in left ventricular end-diastolic diameter (LVIDd) measured by echocardiography between the two groups at 24 months after randomization compared to baseline.
9. Comparison of New York Heart Association (NYHA) functional classification between the two groups at 24 months after randomization.
10. Comparison of Kansas City Cardiomyopathy Questionnaire (KCCQ) scores between the two groups at 24 months after randomization.
11. Incidence of adverse events related to fexofenadine.

3.9 Safety Assessment

Incidence of serious and non-serious adverse events within 24 months of fexofenadine hydrochloride administration.

Adverse events (AE) include:

1. Cardiac adverse reactions (including tachycardia, palpitations).
2. Nervous system reactions (including headache, somnolence, dizziness).
3. Psychiatric reactions (including sleep disorders, anxiety).

4. Gastrointestinal reactions (including diarrhea, nausea).
5. Immune-related skin reactions (including rash, urticaria, pruritus).

Serious adverse events (SAE) include:

Severe allergic/hypersensitivity reactions (including angioedema, chest tightness, dyspnea, other systemic immediate allergic reactions).

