3.11.6 Data Collection

| Items | Baseline (Before Discharge, ≤3 days) | Follow-up (3 months ±14 days) | Follow-up (6 months ±30 days) | Follow-up (12 months ±30 days) | Follow-up (24 months ±90 days) | Follow-up (60 months ±90 days) |
|--|---|-------------------------------------|-------------------------------------|---|---|---|
| Inclusion/ Exclusion Criteria | O | | | | | |
| Signing of Informed Consent | O | | | | | |
| Medical History Informatio n (Age, gender, height, weight, risk factors, clinical past | O | | | | | |

| | | | | | | |
|--|---|---|---|---|---|---|
| history, NYHA functional status, previous history of heart disease) | | | | | | |
| Medical History Information (Any medical events after enrollment in the trial) | | O | O | O | O | O |
| Medication History* | O | O | O | O | O | O |
| Physical Examination | O | Δ | Δ | Δ | Δ | Δ |
| Vital Signs | O | Δ | Δ | Δ | Δ | Δ |
| Coronary Angiography Images# | O | | | | | |
| Laboratory Examinations (Routine blood test + CRP, liver function, renal | O | | Δ | Δ | Δ | Δ |

| | | | | | | |
|--|---|---|---|---|---|---|
| function, routine lipid profile) | | | | | | |
| 12-lead ECG | O | | Δ | Δ | Δ | Δ |
| Echocardi ographic Results (LVEF%, LVIDd, LVIDs) and Original Images | O | | O | O | O | O |
| NYHA Functional Classificat ion | O | | | | O | O |
| KCCQ Score | | | | | O | O |
| MACE Events | | O | O | O | O | O |
| Drug Distributi on | O | O | O | O | O | |
| Drug- related Adverse Reactions | | O | O | O | O | |
| Medicatio n Adherenc e | | O | O | O | O | |

The timeline for data collection is shown in the table above:

Compulsory coronary angiography or laboratory blood tests during follow-up are prohibited. If a participant experiences an endpoint event, it is recommended to collect ECG and coronary angiography data.

*Medication-related information includes the patient's medication status before admission and after discharge.

O: Mandatory item.

Δ: Non-mandatory but recommended.

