3.12 Statistical Methods

| Primary Endpoint | Statistical Methods | Analysis Time Point |
|--|---|--|
| Incidence of major adverse cardiovascular events (MACE, including cardiac death, non-fatal MI, non-fatal stroke, readmission for heart failure, etc.) within 24 months after randomization | Survival analysis, Kaplan-Meier survival curve, Log-rank test | 24th month after randomization |
| Secondary Endpoints | Statistical Methods | Analysis Time Point |
| All-cause death at 24 and 60 months after randomization | Survival analysis, Kaplan-Meier survival curve, Log-rank test | 24th and 60th months after randomization |
| Recurrent myocardial infarction at 24 and 60 months after randomization | Survival analysis, Kaplan-Meier survival curve, Log-rank test | 24th and 60th months after randomization |
| Stroke at 24 and 60 months after randomization | Survival analysis, Kaplan-Meier survival curve, Log-rank test | 24th and 60th months after randomization |
| Hospitalization for heart failure or outpatient/emergency visits due to worsening heart | Survival analysis, Kaplan-Meier survival curve, Log-rank test | 24th and 60th months after randomization |

| | | |
|--|---|--|
| failure at 24 and 60 months after randomization | | |
| Repeat revascularization driven by angina pectoris at 24 and 60 months after randomization | Survival analysis, Kaplan-Meier survival curve, Log-rank test | 24th and 60th months after randomization |
| Difference in left ventricular ejection fraction (LVEF%) measured by echocardiography compared to baseline after randomization | T-test, Wilcoxon rank-sum test | 24th month after randomization |
| Difference in left ventricular end-systolic diameter/body surface area% measured by echocardiography compared to baseline after randomization | T-test, Wilcoxon rank-sum test | 24th month after randomization |
| Difference in left ventricular end-diastolic diameter/body surface area% measured by echocardiography compared to baseline after randomization | T-test, Wilcoxon rank-sum test | 24th month after randomization |
| NYHA functional classification at 12 and 24 months after randomization | Wilcoxon rank-sum test, Chi-square test | 24th month after randomization |
| KCCQ score at 12 and 24 months after randomization | T-test, Wilcoxon rank-sum test | 24th month after randomization |
| Incidence of drug-related adverse events | Chi-square test | 1st, 3rd, 6th, 12th, and 24th months after randomization |

4. Sample Size Calculation

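### The only between-arm safety test the protocol states covers drug-related events, although section 3.9 names all serious and non-serious adverse events; its month-1 time point has no visit

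*Protocol*

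**What the plan says.** **Scope.** Protocol section 3.9 opens with "Incidence of serious and non-serious adverse events within 24 months of fexofenadine hydrochloride administration". It then lists five classes of adverse event, each worded as a reaction. Section 3.8, item 11, is narrower: "Incidence of adverse events related to fexofenadine". In the schedule (3.11.6) the dedicated row is "Drug- related Adverse Reactions", mandatory at months 3, 6, 12 and 24. In the table in 3.12 the one safety row is "Incidence of drug-related adverse events", tested by chi-square.

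**Recording.** Section 7.1 requires every adverse event to be entered in the CRF. The schedule also has a mandatory medical-history row, "Any medical events after enrollment in the trial", at months 3, 6, 12, 24 and 60.

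**Timing.** Section 3.12 sets the safety analysis at the "1st, 3rd, 6th, 12th, and 24th months after randomization". The earliest follow-up column in the schedule is "Follow-up (3 months ±14 days". Sections 3.3, 3.6 and 3.11.5 list months 6, 12, 24 and 60 only.

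**Seriousness.** The serious events described in 3.9 are "Severe allergic/hypersensitivity reactions (including angioedema, chest tightness, dyspnea, other systemic immediate allergic reactions", introduced as an open list. Section 7.2 manages the same category. Section 7.1 makes seriousness the trigger for immediate notification and 24-hour reporting to regulators.

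**The concern.** An analyst who follows 3.12 as written tests a narrower outcome than 3.9 names. The test then depends on a causality judgment for which the protocol gives neither an assessor nor a method. The clinical event committee in 8.2 decides whether a participant continues, and the investigator in 7.1 decides on study drug after an SAE. Neither is given the task of judging relatedness.

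A relatedness filter is most likely to remove events that nobody expects the drug to cause. A bleed, or a hepatic or renal event leading to admission, would be recorded, but if not attributed to the drug it would enter no comparison stated here. This matters in this trial because section 1 says safety in acute myocardial infarction is not yet clear. The long-term data cited in 3.11.4 are one-year data in healthy volunteers, while treatment here lasts 24 months.

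The month-1 time point raises a practical question: no visit collects data then. On seriousness, centers that cannot find a general criterion may send different events through 7.1.

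**Working it through.** No stated figure needs to be reproduced. The check sets the passages side by side.

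**1. Which events does each place cover?**

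| Place | Limited to drug-related? | Role |
|---|---|---|
| 3.9, opening sentence | No | Safety outcome |
| 3.8, item 11 | Yes | Secondary endpoint |
| 3.11.6, adverse-reaction row | Yes | Data collection |
| 3.11.6, medical-events row | No | Data collection |
| 7.1 | No | Recording in the CRF |
| 3.12, safety row | Yes | Between-arm test |

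The unrestricted entries are an outcome statement and two recording rules. The only entry that compares arms is restricted.

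**2. How many comparisons concern safety?** Table 3.12 has 1 primary + 11 secondary = 12 endpoint rows. One of the 12 is a safety row, and it is limited to drug-related events.

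**3. What falls outside every stated comparison?** Start from all adverse events. Remove those judged drug-related, which the safety row compares. Remove death, infarction, stroke, worsening heart failure and angina-driven revascularization, which 3.8 items 1 to 5 and their rows in 3.12 compare whatever the cause. What remains is non-MACCE events not attributed to the drug. The protocol gives no rate for these, so the remainder cannot be counted.

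**4. Is the loss bias or sensitivity?** Under 3.11.3 neither participants nor investigators know the assignment. While the blind holds, errors in judging relatedness do not favor either arm. The filter can still discard real excess events, so the loss is in the ability to detect harm.

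**5. Time points.**
- Safety analysis in 3.12: {1, 3, 6, 12, 24}
- Schedule follow-up columns: {3, 6, 12, 24, 60}
- Sections 3.3, 3.6 and 3.11.5: {6, 12, 24, 60}

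Four of the five analysis points have a schedule column, and three of five also appear in 3.3, 3.6 and 3.11.5. Month 1 is in none of them. Month 3 is in the schedule only.

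**6. Can the wider comparison use data already planned?** The adverse-reaction row is mandatory at four visits (3, 6, 12, 24). The medical-events row is mandatory at all four of these. No new visit is needed.

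**The case against.** The strongest reply is that nothing here conflicts. Table 3.12 is a table of endpoints, and its last row simply carries endpoint 11. Section 3.9 is a separate assessment that names an incidence and promises no test, and a statistical analysis plan would normally tabulate all adverse events by arm. Much of this stands: a drug-related endpoint and a broader assessment can coexist, and table layouts belong in the SAP. It does not remove the point. The protocol chose to state a safety comparison, and the one it states is narrower than the outcome it names and rests on an unassigned judgment.

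Three stronger readings are tempting, and the document does not support them.

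- **Unrelated events go uncollected.** Section 7.1 and the mandatory medical-events row both capture them.
- **The protocol has no seriousness criterion.** The list in 3.9 is open, 5.1 names GCP and ICH (as what audits check against), and the reporting figure in 7.1 is not shown in the text available. Only the readable text can be said to lack a general criterion.
- **The gap can be sized from the expected number of MACCE.** Section 4's rates would give 1402 × 0.165 + 1402 × 0.132 ≈ 416 patients. Those events are already compared as efficacy endpoints, so they do not measure the gap, and section 4 states no time horizon for the rates.

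Two further replies have some weight. Section 8.2 says the safety of the marketed drugs is established, but that does not settle safety in acute infarction, which section 1 leaves open. And a month-1 analysis does not strictly need a visit: cumulative incidence can be recovered later if onset dates are recorded, which the protocol does not say.

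**Conclusion.** The point holds in limited form, at minor to moderate severity. The safety outcome in 3.9 covers all serious and non-serious events, while endpoint 11, the adverse-reaction row and the only stated safety test cover drug-related events. Non-MACCE events not attributed to the drug are therefore recorded but left out of every between-arm comparison in this protocol. The consequence is reduced sensitivity to unexpected harm. It is not bias, provided the blind holds, and the primary efficacy inference is untouched. The number of events affected cannot be estimated from the document.

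The timing mismatch is definite but small: month 1 has no visit, and month 3 appears only in the schedule. Seriousness is a secondary point for the sponsor to confirm, because the 7.1 figure could not be read. The conclusion concerns what the protocol states; an SAP that was not available may already compare all events.

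**What to change.** 1. **Comparison.** In 3.12, add a comparison by arm of all AEs and of all SAEs through 24 months, regardless of attribution. Keep endpoint 11 as the drug-related subset, and state that the blinded investigator records causality. Align 3.8 item 11, 3.9 and the schedule row with this.
2. **Time points.** Either drop month 1 from the safety row or define it as cumulative incidence from recorded onset dates. Make 3.3, 3.6 and 3.11.5 agree with the schedule on month 3.
3. **Seriousness.** The sponsor should confirm that a general seriousness criterion applies to SAE classification (5.1 already names GCP and ICH) and reconcile 3.9 with 7.1, including how MACCE endpoint events are handled. Section 7.1 also ties SAEs to a decision on study drug, so the sponsor should confirm which events that sentence is meant to cover. No change to treatment or dosage rules is proposed.

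The cost is a protocol amendment, a causality entry in the CRF if there is none, somewhat more event coding and one more analysis row. No new visits or procedures are needed. Any added SAE reporting depends on how item 3 is settled.

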3.10 Enrollment

All patients with acute ST-segment elevation myocardial infarction will be screened for eligibility to participate in this study. Members of each study team will review the patient's medical history to determine compliance with inclusion and exclusion criteria. If eligible, the patient can be registered and enrolled in the study after signing the written informed consent form. Prior to collecting study data, participants will be informed of study details, including: (1) this is an investigator-initiated clinical study; (2) participation is voluntary, and there will be no penalty for withdrawal; (3) potential risks and benefits of participation. Vulnerable populations will be excluded in accordance with the inclusion and exclusion criteria.

3.11 Study Methods

3.11.1 Study Design

Patients with acute ST-segment elevation myocardial infarction will be randomly assigned in a 1:1 ratio to the placebo group or the fexofenadine hydrochloride group for efficacy and safety assessment.

3.11.2 Randomization Method

Eligible patients will be randomly assigned to the placebo group or the fexofenadine hydrochloride treatment group in a 1:1 ratio after recruitment, with the randomization process conducted via an online system by the research institution.

3.11.3 Study Blinding

Drugs in the placebo group and the treatment group are identical in appearance and packaging, and participants are unaware of their group assignment. Throughout the study, blinding will be maintained during the generation of the randomization code, drug coding, patient medication administration, data monitoring, data management, and statistical analysis, and investigators are unaware of the patients' group assignments and medication status.

3.11.4 Drug Treatment

Patients in both groups will receive current standard drug therapy in accordance with the 2023 European Society of Cardiology (ESC) Guidelines for the Management of Acute Coronary Syndromes, including dual antiplatelet therapy with aspirin/indobufen + ticagrelor/clopidogrel, statins for lipid-lowering, metoprolol, ACEI/ARB drugs for anti-cardiac remodeling, etc., with updates in line with guideline revisions. On this basis, additional treatments are as

follows:

Fexofenadine hydrochloride group: Fexofenadine hydrochloride tablets, 60 mg, twice daily, orally for 24 months.

Placebo group: White starch tablets identical in appearance and packaging, twice daily, orally for 24 months.

Treatment initiation time: Immediately after randomization.

After providing informed consent, enrolled patients will be randomly assigned to receive fexofenadine hydrochloride or placebo. The fexofenadine hydrochloride group will receive 60 mg BID orally for 24 months. Patients assigned to the placebo group will receive identically appearing starch tablets orally for 24 months.

Note: The usual dose of fexofenadine hydrochloride for the treatment of seasonal allergic rhinitis and chronic idiopathic urticaria is 60 mg bid. Large-scale randomized controlled clinical studies have shown that long-term use (1 year) of different doses of fexofenadine hydrochloride (20-240 mg QD) has no significant safety impact on healthy volunteers.

